4.4 Exclusion criteria

Subjects must not fulfill any of the following exclusion criteria. It is not permitted to waive any of the criteria for any subject:

Pregnancy and Breastfeeding

- 1. Lactating or pregnant women.
- 2. Subjects wishing to parent a child during the study.

MS disease

- 3. Evidence of a relapse of MS with onset within 30 days prior to baseline EDSS assessment or between baseline EDSS assessment and randomization [see Section 6.1.1].
- 4. Presenting with a diagnosis of MS with progressive course from onset (i.e., primary progressive MS or progressive relapsing MS).

5 December 2018, page 81/376

Treatments

- 5. Treatment with the following medications within 7 days prior to randomization:
 - IFN β -1a, IFN β -1b, or glatiramer acetate
- 6. Treatment with the following medications within 15 days prior to randomization:
 - β -blockers, diltiazem, verapamil, digoxin or any other anti-arrhythmic or HR • lowering systemic therapy [non-exhaustive list of drugs provided in Appendix 4]
 - Cholestyramine or activated charcoal
- 7. Treatment with the following medications within 30 days prior to randomization:
 - Adrenocorticotropic hormone (ACTH) or systemic corticosteroids (for any reason)
 - Dimethyl fumarate
 - Vaccination with live vaccines
- 8. Treatment with the following medications within 90 days prior to randomization:
 - Plasmapheresis, cytapheresis
 - i.v. immunoglobulin •
 - Treatment with an investigational drug (within 90 days or five half-lives of the drug, whichever is longer), except biological agents (see below)
- 9. Treatment with the following medications within 180 days prior to randomization:
 - Azathioprine, methotrexate, or cyclophosphamide
 - Natalizumab •
 - Other systemic immunosuppressive treatment (e.g., cyclosporine, sirolimus, • mycophenolic acid)
 - Non-lymphocyte-depleting experimental biological agents (e.g., daclizumab)
- 10. Treatment with the following medications within 24 months prior to randomization:
 - Lymphocyte-depleting biological agents such as rituximab or ocrelizumab •
 - Cladribine
- 11. Treatment with the following medications at any time prior to randomization:
 - Alemtuzumab
 - Mitoxantrone, leflunomide, or teriflunomide
 - Fingolimod •
 - Ponesimod •
 - Other investigational S1P modulators
 - Stem-cell transplantation

Infection and Infection Risk

12. Ongoing known bacterial, viral or fungal infection (with the exception of onychomycosis and dermatomycosis), positive hepatitis B surface antigen test at Visit 1 (Screening) (unless hepatitis B vaccination has occurred within 4 weeks prior to a positive screening test and a repeat hepatitis B surface antigen test performed \geq 2 weeks after the initial test has been negative) or hepatitis C antibody tests at Visit 1 (Screening).

5 December 2018, page 82/376

- 13. Congenital or acquired severe immunodeficiency or known human immunodeficiency virus (HIV) infection or positive HIV testing at Visit 1 (Screening).
- 14. Negative antibody test for varicella-zoster virus at Visit 1 (Screening).
- 36. Known Progressive Multifocal Leukoencephalopathy (PML) infection or evidence of new neurological symptoms or MRI signs within 6 months prior to randomization which are compatible with a diagnosis of PML infection

Malignancy

- 15. History or presence of malignancy (except for surgically excised basal or squamous cell skin lesions), lymphoproliferative disease, or history of total lymphoid irradiation or bone marrow transplantation.
- 16. Presence of pre-cancerous (e.g., actinic keratosis, atypical moles) or cancerous skin lesions (e.g., basal cell carcinoma, squamous cell carcinoma) at Visit 2 (Baseline).

Ophthalmologic

17. Presence of macular edema.

Cardiovascular

18. Any of the following cardiovascular conditions:

- Resting HR < 50 bpm as measured by the pre-randomization 12-lead ECG on Day 1
- Myocardial infarction within 6 months prior to randomization or ongoing unstable ischemic heart disease
- Cardiac failure (New York Heart Association class III or IV) or any severe cardiac disease at the time of Visit 1 (Screening) or randomization
- History or presence of valvular heart disease associated with symptoms or • significant hemodynamic change according to investigator judgment
- History or presence of cardiac rhythm disorders (e.g., sino-atrial heart block, • symptomatic bradycardia, atrial flutter or atrial fibrillation, ventricular arrhythmias, cardiac arrest)
- Presence of second-degree AV block Mobitz Type II or third-degree AV block, or a QTcF interval > 470 ms (females), > 450 ms (males) as measured by 12-lead ECG at Visit 1(Screening) or Visit 2 (Baseline) or by the pre-dose ECG at Visit 3 (Randomization / Day 1)
- History of syncope associated with cardiac disorders
- Systemic arterial hypertension not controlled by medication according to the investigator's judgment

Metabolic

19. Type 1 or 2 diabetes that is poorly controlled according to the investigator's judgment, or diabetes complicated with organ involvement such as nephropathy or retinopathy.

5 December 2018, page 83/376

Pulmonary

20. Subjects with a clinically significant pulmonary condition including:

- Asthma that is insufficiently controlled according to the investigator's judgment, or any hospitalization due to asthma exacerbation within 6 months prior to randomization
- Abnormal PFTs: FEV₁ or forced vital capacity (FVC) < 70% of the predicted normal value at Visit 2 (Baseline)
- 21. Active or latent TB, as assessed by CXR performed at Visit 1 (Screening) or within 90 days prior to Visit 1 (Screening), or IFN gamma release assay (QuantiFERON-TB-Gold[®]) at Visit 1 (Screening), except if there is documentation that the subject has received adequate treatment for latent TB infection or TB disease previously

Hematology

- 22. Any of the following abnormal laboratory values at Visit 1 (Screening) or Visit 2 (Baseline):
 - Hemoglobin (Hb) < 100 g/L
 - White blood cell (WBC) count $< 3.5 \times 10^{9}/L$ ($< 3500/mm^{3}$)
 - Neutrophil count < $1.5 \times 10^{9}/L$ (< $1500/mm^{3}$)
 - Lymphocyte count $< 0.8 \times 10^{9}/L (< 800/mm^{3})$
 - Platelet count $< 100 \times 10^{9}/L (< 100,000/mm^{3})$

Hepatic

- 23. Known history of active hepatitis B or C any time prior to randomization or known history of active hepatitis A within 3 years prior to randomization.
- 24. Presence of chronic liver or biliary disease.
- 25. Moderate or severe hepatic impairment defined as Child Pugh Score B or C, respectively, based on measurement of total bilirubin, serum albumin, International Normalized Ratio (INR) and as well as on presence/absence and severity of ascites and hepatic encephalopathy [Appendix 15].
- 26. Any of the following abnormal laboratory values at Visit 1 (Screening) or Visit 2 (Baseline):
 - ALT/SGPT > $2 \times$ the upper limit of normal (ULN)
 - $AST/SGOT > 2 \times ULN$
 - Total bilirubin > $1.5 \times$ ULN (unless in the context of known Gilbert's Syndrome).

Renal

- 27. Hypoproteinemia (e.g., in case of severe liver disease or nephrotic syndrome) with serum albumin < 3.0 g/dL.
- 28. Severe renal insufficiency defined as a calculated creatinine clearance < 30 mL/min (Cockroft-Gault) at Visit 1 (Screening) or Visit 2 (Baseline).

5 December 2018, page 84/376

Other categories

- 29. Known history of clinically significant drug or alcohol abuse.
- 30. Known allergy to any of the ponesimod formulation excipients.
- 31. Known allergy to any of the Aubagio[®] formulation excipients.
- 32. Known hereditary problems of galactose intolerance (e.g., Lapp lactase deficiency, glucose-galactose malabsorption).
- 33. Any other clinically relevant medical or surgical condition, which, in the opinion of the investigator, would put the subject at risk by participating in the study.
- 34. Contraindications for MRI such as:
 - Pacemaker, any metallic implants such as artificial heart valves, aneurysm/vessel • clips and any metallic material in high-risk areas which are contraindicated for MRI according to the local procedures
 - Known allergy to any gadolinium (Gd)-containing contrast agent
 - Claustrophobia if its nature or severity is prohibitive for performing MRI according to the investigator's judgment
- 35. Subjects unlikely to comply with protocol, e.g., uncooperative attitude, inability to return for FU visits, or known likelihood of not completing the study including mental condition rendering the subject unable to understand the nature, scope, and possible consequences of the study.

4.5 Subjects of reproductive potential

WOCBP and fertile male subjects participating in the study must agree that they will take means to reduce reproductive risk as defined in the following sections.

4.5.1 Women of childbearing potential

A woman is considered to be of childbearing potential unless she meets at least one of the following criteria:

- Previous bilateral salpingo-oophorectomy or hysterectomy. •
- Premature ovarian failure confirmed by a specialist. •
- XY genotype, Turner syndrome, uterine agenesis. •
- Postmenopausal, defined as 12 consecutive months with no menses without an • alternative medical cause (ICH M3 definition).

WOCBP participating in the study must agree to use one of the following reliable methods of contraception from the Visit 1 (Screening) until 6 weeks after the first of two consecutive tests showing teriflunomide plasma level < 0.02 mg/L:

- Two methods of contraception, one from Group 1 and one from Group 2, defined as • follows:
 - Group 1: Oral, implantable, transdermal or injectable hormonal contraceptives or intrauterine devices. If a hormonal contraceptive is chosen from this group,

5 December 2018, page 85/376

it must be taken for at least 30 days prior to randomization. Non hormonal methods of contraception (e.g., intrauterine device) should be in place no later than Visit 2 (Baseline).

- Group 2: Female or male condoms, diaphragm or cervical cap.

OR

- True abstinence from intercourse with a male partner only when this is in line with the preferred lifestyle of the subject.
 - OR
- Permanent female sterilization (tubal occlusion/ligation at least 6 weeks prior to Visit 1 [Screening]).
 OR
- Sterilization of the male partner with documented post-vasectomy confirmation of the absence of sperm in the ejaculate.

Rhythm methods or the use of a condom by a male partner alone are not considered acceptable methods of contraception for this study.

The methods of contraception used (including non-pharmacological methods) must be recorded in the eCRF. At all visits and 4-weekly telephone calls the methods of contraception will be reviewed and the contraceptive method form entered in the eCRF must be updated as applicable.

4.5.2 Fertile male subject

A fertile male is defined as physiologically capable of conceiving an offspring.

Since teriflunomide is detected in semen [Aubagio[®] USPI, Aubagio[®] SmPC], fertile male subjects participating in the study who are sexually active with WOCBP must agree to use a condom during the treatment period and for up to 6 weeks after the first of two tests showing teriflunomide plasma level < 0.02 mg/L and agree not to father a child during this period. The female partners of the fertile male subjects, if WOCBP, will need to use effective methods of contraception [Aubagio[®] USPI, Aubagio[®] SmPC], as assessed by the investigator during the same period.

4.6 Medical history

Relevant medical history, as defined below, must be recorded in the eCRF:

- Significant chronic medical conditions at any time prior to the study (in the opinion of the investigator)
- Cardiac, cardiovascular, pulmonary, liver, renal, eye disorder, and skin conditions, peripheral edema, serious infections leading to hospitalization, and malignant tumors at any time prior to the study

5 December 2018, page 86/376

- Medically significant new acute medical conditions in the past 24 months prior to the • study (in the opinion of the investigator)
- Smoking status at the time of entry in the study.

Previous and concomitant therapies at Baseline, as defined in Section 5.2, will be recorded in the eCRF.

MS disease characteristics, evidenced by documentation in the patient charts, as defined below, will be recorded on the MS history page of the eCRF:

- Date of first MS symptoms •
- Date of MS diagnosis •
- MS type (e.g., RRMS, SPMS) •
- Complication or symptoms associated with MS (e.g., optic neuritis, numbness, • spasticity, tremor, fatigue, dizziness, dysfunctional bladder, cognitive problems, etc.) within the last 24 months prior to the study
- Number of documented MS relapses within the last 12 months and between 12 and • 24 months prior to the study. The onset and resolution date, and treatment of these relapses (corticosteroids, ACTH, plasmapheresis etc.) will also be reported.
- Number of documented Gd+ lesions per scan and number of documented • T2 hyperintense lesions per scan on any MRI scan performed within 24 months prior to the study. Additionally, the condition of the MRI scan will be collected (e.g., scanner type, manufacturer and strength, the type of T1 sequence and number of slices used to detect Gd+, contrast agent used [Gd type], dose of contrast agent and time of injection, time of T1 sequence, the type of T2 sequence and number of slices used to detect T2 hyperintense lesions).
- Previous MS disease-modifying treatments received at any time in the past. The start • date, end date, dose, route, frequency, and reason for discontinuation will be recorded in the eCRF.

TREATMENTS 5

5.1 Study treatment

The treatment period consists of an up-titration period (from Day 1 to 14) and a maintenance period (Day 15 until EOT).

During an initial phase of the study, the study drugs in the up-titration period will be administered in a double-dummy fashion. Ponesimod (or matching placebo) will be presented as tablet, and teriflunomide 14 mg (or matching placebo) will be presented as capsule (i.e., daily administration of one tablet and one capsule). At a later phase, the

double-dummy material (tablet and capsule) will be replaced by the daily administration of one capsule containing either ponesimod or teriflunomide.

In the maintenance period, the study treatment consists of the daily administration of one capsule containing ponesimod 20 mg or teriflunomide 14 mg.

If the subject expresses any concern regarding her/his ability to swallow the medicine, she/he will be shown an example of a capsule to be used in the study and will be given the option to perform a swallowing test with a placebo capsule at Visit 2 (Baseline) in order to test future compliance with study drug intake requirements. The test is to be done under the supervision of the site personnel.

5.1.1 Investigational treatment: description and rationale

Ponesimod is supplied as its free base, in oral film-coated tablets at the doses of 2, 3, 4, 5, 6, 7, 8, 9, 10, and 20 mg. The 20-mg tablet is over-encapsulated. During an initial phase of the study, one tablet of ponesimod 2, 3, 4, 5, 6, 7, 8, 9, or 10 mg (or matching placebo) will be taken orally o.d. during the up-titration period (Day 1 to 14). The matching placebos for the doses of 2, 3, 4, 5, 6, 7, 8, 9, and 10 mg are supplied as identical tablets, formulated with the same excipients but without the active ingredient, ponesimod tablets for the up-titration is completed, one capsule of 2, 3, 4, 5, 6, 7, 8, 9, and 10 mg ponesimod tablets for the up-titration is completed, one capsule of 2, 3, 4, 5, 6, 7, 8, 9, and 10 mg ponesimod (or matching teriflunomide 14 mg) will be taken orally o.d. during the up-titration period. During the maintenance period, one capsule of ponesimod 20 mg (or matching teriflunomide 14 mg) will be taken orally o.d.

Based on the available data and considering the currently available therapeutic options, ponesimod 20 mg displays the optimal benefit-risk balance for further development in RMS.

Lower doses of ponesimod are unlikely to provide an adequate level of disease control and do not offer a relevantly improved safety profile. Consistent with a lower effect on lymphocytes, 10 mg ponesimod was unable to suppress MRI brain inflammatory activity to the level achieved with 20 mg and continued to show higher levels of clinical disease activity with more relapses and accumulation of disability after 3 years of treatment. While less efficacious, 10 mg showed similar rates of AEs and discontinuations when compared to 20 mg [see Sections 1.3.2.3 and 1.3.2.4].

Doses higher than 20 mg were associated with decreased tolerability; there were increased discontinuation rates with 40 mg mainly due to higher pulmonary function effects and increased incidence of liver enzyme elevations. By contrast, there was a similar or small incremental effect of 40 mg compared to 20 mg on lymphocytes, MRI brain inflammatory activity, and clinical disease activity [see Sections 1.3.2.3 and 1.3.2.4].

Ponesimod / ACT-128800 Relapsing multiple sclerosis Protocol AC-058B301, OPTIMUM Version 7 5 December 2018, page 88/376

Confidential

5.1.2 Comparator and matching placebo: description and rationale

Teriflunomide is supplied for this study as film-coated tablets as the commercially available Aubagio[®] tablets. Each tablet contains 14 mg of teriflunomide and excipients. Teriflunomide tablets are over-encapsulated. The study treatments of the up-titration period are administered in a double-dummy fashion, one capsule of teriflunomide or matching placebo will be taken orally o.d. during up-titration (Days 1 to 14). Matching placebo capsules will contain only a filling excipient.

In the maintenance period, study treatment always consists of the daily oral administration of one capsule containing teriflunomide or ponesimod (i.e., no double-dummy). The dose and regimen of teriflunomide are in accordance with the product labeling of Aubagio[®] [Aubagio[®] USPI, Aubagio[®] SmPC]. Aubagio[®] is manufactured by Sanofi.

Two dosage forms of Aubagio[®], 7 mg and 14 mg, have been approved in US, while only 14 mg has been approved in the EU and other countries such as Australia. The reduction in relapse rates observed in the Phase 3 studies were comparable between the two doses, but the 7 mg dose has failed to demonstrate an effect on accumulation of disability. Teriflunomide 14 mg appears to be an appropriate comparator for ponesimod 20 mg. Demonstration of superiority over teriflunomide 14 mg in terms of ARR is clinically relevant, as it would provide evidence of significant benefit of the new investigational drug compared to a world-wide approved, effective, first-line oral therapy that has been shown to reduce relapse rate and accumulation of disability.

5.1.3 Study treatment administration

5.1.3.1 Titration

A gradual up-titration of ponesimod from a 2 mg starting dose to a 20 mg maintenance dose over a period of 14 days was found to successfully mitigate first-dose effects. This 2-week up-titration regimen will be implemented in the study on initiation of treatment (Day 1) and on days of re-initiation of treatment following treatment interruption of more than 3 days [see Section 5.1.9].

In order to keep the blind of the study, subjects randomized to teriflunomide will undergo a mock up-titration.

Duration Dose regimen in the Dose level **Treatment** ponesimod group period Titration Days 1 and 2 1 and 2 2 mg Titration Days 3 and 4 3 and 4 3 mg Titration Days 5 and 6 5 and 6 4 mg Titration Day 7 5 mg 7 Titration Day 8 8 6 mg 9 Titration Day 9 7 mg Titration Day 10 10 8 mg Titration Day 11 9 mg 11 Titration Days 12 to 14* 10 mg 12 to 14 Maintenance Day 15 until EOT 20 mg NA

Table 4Dosing scheme

* = Visit 4 is to take place at Day 15 ± 1 day. The titration kit will therefore include an additional capsule and tablet (if applicable) for treatment on Day 15 (i.e., dose regimen in the ponesimod group = 10 mg).

EOT = End-of-Treatment; NA = not applicable.

Study drug up-titration, other than described above, is prohibited. Study drug down-titration is not foreseen in any situation and is prohibited.

One tablet and one capsule (during the double-dummy phase) or one capsule will be taken orally o.d., in the morning, either with breakfast or before or after breakfast, preferably at approximately the same time each day. The capsule and tablet will be swallowed as a whole. When applicable, the tablet and the capsule (during double-dummy phase) will be taken in the shortest time from each other with no predefined order (tablet or capsule can be taken first). The last administration date and time of study drug (tablets and capsules) prior to the study visits and the administration date and time of study drug (tablets and capsules) on the days of visits will be recorded in the eCRF.

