5.1.9 Study treatment dose adjustments and interruptions

Study drug up-titration, other than described in Section 5.1.3, is prohibited. Study drug down-titration is not foreseen in any situation and is prohibited.

Study drug interruption should be avoided. If study treatment intake is interrupted by the subject for any reason, she/he must immediately inform the investigator/treating neurologist.

Study treatment may be temporarily interrupted in response to an AE, a diagnostic or therapeutic procedure, a laboratory abnormality, or for administrative reasons. Study-specific criteria for interruption of study treatment are described in Section 5.1.13. The duration of an interruption is determined by the investigator and is not limited in time. At maximum, it will last until the investigator deems the subject necessary to require another MS treatment. In this event, it is recommended performing an accelerated elimination procedure [see Section 5.1.14] before a new immunomodulatory treatment for MS is started.

Detailed guidance on how to re-initiate study drug in the event of drug interruption is provided in Section 5.1.10.

Study treatment dose adjustments/interruptions must be recorded in the eCRF.

5.1.10 Guidance for re-initiation of study treatment in the event of study treatment interruption

If study drug intake is interrupted by the subject for any reason, she/he must immediately inform the principal investigator / treating neurologist.

The following guidance is provided for re-initiation of investigational study drug after study drug interruptions.

A schematic overview of the re-initiation algorithm is given below in Figure 5.

Depending on the day, time, and duration of study drug interruption, the following procedures will be followed.

- If the subject missed taking the dose in the morning:
 - The dose should be taken at any time on the same day.
 - Regular dosing should be continued with the morning dose on the following day.
- If the subject missed taking the dose for one or more days during treatment up-titration (from 1 to 14 days after the first-dose of initiation/re-initiation of the study drug):

5 December 2018, page 97/376

- The original up-titration scheme needs to be re-applied, with the initial dose and gradual up-titration steps for 14 days after the first-dose of re-initiation of the study drug.

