- On the day of the re-initiation of investigational study drug, the subject must be monitored for at least 4 h post-dose by the first-dose administrator, following the cardiac assessment schedule and applying the discharge criteria as described for Day 1 [see Section 5.1.11].
- If the subject missed taking the dose for up to three consecutive days during treatment maintenance (from 14 days after the first dose of initiation/re-initiation of the study drug onwards):
 - Dosing should be continued in the morning following the last day without investigational study drug intake, with the same dose taken prior to study drug interruption.
 - Study drug intake may be re-initiated by the subject at home.
 - Subjects must be instructed to contact the investigator immediately if they experience any symptoms of bradycardia (e.g., dizziness, vertigo, syncope).
- If the subject missed taking the dose for four or more consecutive days during treatment maintenance (from 14 days after the first dose of initiation/re-initiation of the study drug onwards):
 - The original up-titration scheme for the investigational study drug needs to be re-applied.
 - On the day of the re-initiation of treatment, the subject must be monitored for at least 4 h post-dose by the first-dose administrator, following the cardiac assessment schedule and applying the discharge criteria as described for Day 1 [see Section 5.1.11].

Whenever the investigator / treating neurologist becomes aware that the subject did not report having missed the study drug intake for one or more days during up-titration or four or more days during maintenance and has continued dosing, the subject should be interviewed by the investigator / treating neurologist for any symptoms related to bradycardia and further examinations (e.g., 12-lead ECG, BP measurement) may be performed at the discretion of the investigator / treating neurologist. Based on an assessment of the clinical findings and the likelihood of subject's adherence to treatment, the investigator / treating neurologist will determine whether the subject can continue regular dosing, need to re-initiate treatment, or should permanently discontinue treatment.

Ponesimod / ACT-128800 Relapsing multiple sclerosis Protocol AC-058B301, OPTIMUM Version 7 5 December 2018, page 98/376

Confidential

5.1.11 Criteria for discharge from cardiac monitoring on Day 1, and on the first day of re-initiation of the investigational study drug following treatment interruptions

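### The triggers for restarting titration after missed doses conflict between Sections 5.1.3.1 and 5.1.10, and the two phase windows in 5.1.10 share one day

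*Protocol*

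**What the plan says.** Section 5.1.3.1 applies the two-week titration at the start of treatment and again "on days of re-initiation of treatment following treatment interruption of more than 3 days". It does not distinguish titration from maintenance, and its cross-reference is to Section 5.1.9. It adds: "Study drug up-titration, other than described above, is prohibited". Section 5.1.9 repeats this ("Study drug up-titration, other than described in Section 5.1.3, is prohibited"), gives no threshold itself, and sends the reader to 5.1.10 for detail.

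Section 5.1.10 sets rules by phase, with both windows counted from initiation or re-initiation:

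- Titration: "If the subject missed taking the dose for one or more days during treatment up-titration (from 1 to 14 days after the first-dose" of initiation or re-initiation), then "The original up-titration scheme needs to be re-applied, with the initial dose and gradual up-titration steps for 14 days", and on that day "the subject must be monitored for at least 4 h post-dose by the first-dose administrator".
- Maintenance, short gap: "If the subject missed taking the dose for up to three consecutive days during treatment maintenance (from 14 days after the first dose" of initiation or re-initiation, onwards), dosing continues "with the same dose taken prior to study drug interruption", and the subject may resume at home.
- Maintenance, four or more consecutive days: the scheme is re-applied, with the same monitoring.

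Section 5.1 and Table 4 place titration on Days 1 to 14 and maintenance from Day 15. Table 4 gives 10 mg on Days 12 to 14 and 20 mg from Day 15. Its footnote notes that Visit 4 falls on Day 15 ± 1 day and provides an extra titration-kit dose for Day 15, equal to 10 mg in the ponesimod group.

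**The concern.** Two sections give different triggers for the same procedure, and two rules within one section claim the same day. Section 1.3.2.4 describes transient heart-rate and AV-conduction changes as the most prominent safety-related signal. Titration and monitored re-initiation are there to limit those effects.

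Which rule a site follows decides whether a subject is restarted and monitored for at least 4 h. It can also decide treatment status: under 5.1.11 and 5.1.13.1, a subject who has not met the discharge criteria 12 h after a re-initiation dose must stop study drug permanently. Section 6.2 makes ECG findings on re-initiation days a safety endpoint, so the rule applied also determines who contributes those data. About 200 sites work from this text.

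**Working it through.** The protocol gives no figure to reproduce here. The check sets the rules against each other by day and by length of gap.

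**Convention.** Day 1 is the day of first dose, so k days after first dose is Day 1 + k.

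**Windows in 5.1.10.**
- Titration rule: k = 1 to 14, so Days 2 to 15.
- Maintenance rule: k = 14 onwards, so Day 15 onwards.
- Overlap: 1 + 14 = 15, so Day 15 only.

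If 14 days after first dose is read loosely as Day 14, the overlap moves to Day 14 and is still one day. Because both windows also count from re-initiation, the shared day recurs after every restart.

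**Rules applied to each gap.**

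| Missed days | Gap starts | 5.1.3.1 | 5.1.10, titration rule | 5.1.10, maintenance rule |
|---|---|---|---|---|
| 1 to 3 | Days 2–14 | no restart (implied) | restart, at least 4 h monitoring | does not apply |
| 1 to 3 | Day 15 | no restart (implied) | restart, at least 4 h monitoring | continue, may be at home |
| 1 to 3 | Day 16 on | no restart (implied) | does not apply | continue, may be at home |
| 4 or more | Days 2–14 | restart | restart, at least 4 h monitoring | does not apply |
| 4 or more | Day 15 | restart | restart, at least 4 h monitoring | restart, at least 4 h monitoring |
| 4 or more | Day 16 on | restart | does not apply | restart, at least 4 h monitoring |

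The first two rows conflict and the other four agree. In the first row the conflict is between sections: a subject who misses only Day 8 is restarted under 5.1.10 and not under 5.1.3.1. In the second row it lies inside 5.1.10: a subject who misses only Day 15 meets both of its rules.

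**Dose at the boundary.** For a gap of 1 to 3 days starting on Day 15, the last dose taken was that of Day 14, which is 10 mg in Table 4. The dose scheduled from Day 15 is 20 mg, yet the footnote foresees 10 mg on Day 15 from the titration kit. The maintenance rule's reference to the dose taken before the gap therefore points to 10 mg, while the schedule points to 20 mg or, on Day 15 itself, to either.

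**Other text on the thresholds.** The electronic diary rule in 5.1.8.2 tells the subject to contact the investigator after 1 or more missed doses in titration, or 4 or more in maintenance. The paragraph in 5.1.10 on unreported missed doses uses the same two thresholds. Both match the phase-specific rules of 5.1.10, so 5.1.3.1 is the outlier.

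**The case against.** The best defence is that 5.1.3.1 is a one-sentence introduction and 5.1.10 is the operative text. Section 5.1.9 directs the reader there, and the diary rule and the unreported-miss paragraph agree with it. A subject who misses one titration dose is prompted by the diary to call before the next dose. This stands in part: it makes it likely that many sites would follow 5.1.10 within titration. It does not remove the conflicting threshold from the dosing section. It also does nothing for the shared day or the dose wording, which lie inside 5.1.10 and Table 4.

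A second defence is that Section 5.1 and Table 4 put Day 15 in maintenance, so the overlap can be read away. That is a reasonable inference, but the titration window in 5.1.10 still includes the day. Figure 5, the re-initiation algorithm, is not shown in the available text and may settle the boundary.

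Three stronger readings are tempting and are not supported:

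- A reader might infer that a missed dose anywhere in titration leads either to a monitored restart or to resumption at home. Section 5.1.3.1 only implies that no restart is needed and does not mention home dosing. That explicit choice arises only on the shared day.
- A reader might infer that the ban on other up-titration forbids the restart in 5.1.10 after 1 to 3 missed days. Section 5.1.10 re-applies the original scheme, so the ban reads more naturally as excluding other dose schedules.
- A reader might take Day 15 to be unequivocally a 20 mg day. The Table 4 footnote says otherwise.

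**Conclusion.** The inconsistency is real and should be corrected, because following the stated rules literally gives conflicting instructions on monitored re-initiation. It has three parts: the trigger for gaps of 1 to 3 days in titration (5.1.3.1 against 5.1.10), one day shared by the two windows in 5.1.10, and an unclear dose on resumption at that same boundary. It does not extend to gaps of 4 or more days. From Day 16 after the first dose, the restart triggers agree.

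Placing the overlap on Day 15 assumes that Day 1 is the first dose. The other reading moves the overlap by one day without removing it. The number of subjects affected is unknown, and Figure 5 could not be checked. The point concerns safety conduct and the re-initiation ECG endpoints; nothing here bears on the primary or secondary efficacy tests. That most of the text agrees with 5.1.10 does not show which rule is clinically right, and no view is taken on that.

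**What to change.** Reconcile 5.1.3.1 (including its cross-reference), 5.1.9, 5.1.10, Table 4 with its footnote, and Figure 5, so that together they state:

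- one restart threshold for each phase;
- phase days that do not overlap, counted from initiation and from re-initiation in the same way;
- one reading of which dose is resumed when a gap touches the change from titration to maintenance, consistent with the Table 4 footnote.

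The sponsor's safety physicians must decide which threshold, boundary and dose govern. The cost is protocol wording in these places and a memo to sites, with no new procedures or assessments.
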